# 1.1.3. Flecainide

Flecainide is a class 1C antiarrhythmic drug that blocks sodium channels. Flecainide is used to suppress cardiac tachyarrhythmias including paroxysmal atrial fibrillation and supraventricular tachycardia. Flecainide is also used to treat LQT3 patients and patients with Ca2+-mediated, catecholaminergic polymorphic ventricular tachycardia (CPVT). Flecainide can have proarrhythmic effects after myocardial infarction (Echt et al. 1991). These divergent actions result from its physiological and pharmacological actions at multiple, levels of cellular organization (Salvage et al. 2017). These properties of flecainide were studied in murine genetic models with modified Nav channel or intracellular ryanodine receptor (RyR2)-Ca2+ channel function (Watanabe et al. 2009). Flecainide accesses its transmembrane Nav1.5 channel binding site during activated, open states, producing a use-dependent antagonism. Closing either activation or inactivation gates traps flecainide within the pore. An early peak INa related to activation of Nav channels followed by rapid de-activation, causes action potential upstrokes and their propagation. This is diminished in pro-arrhythmic conditions reflecting loss of function of Nav1.5 channels, such as in the Brugada syndrome that may be exacerbated by flecainide. In contrast, the pro-arrhythmic effects attributed to prolonged action potential recovery by abnormal late INaL following gain-of-function modifications of Nav1.5 channels in LQT3 are reduced by flecainide. Anti-arrhythmic effects of flecainide that reduce triggering in CPVT mediated by sarcoplasmic reticular Ca2+ release could arise from its primary actions on Nav channels indirectly decreasing [Ca2+]i by a reduced [Na+]i and/or direct open state antagonism of the RyR2-Ca2+ channel. The consequent [Ca2+]i alterations could also modify action potential propagation velocity and therefore arrhythmic substrate through its actions on Nav1.5 channel function. This is consistent with the paradoxical differences between flecainide actions on Na+ currents, AP conduction and arrhythmogenesis under circumstances of normal and increased RyR2 function.

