# 3. CHARACTERISTICS OF THE RESEARCH POPULATION

## 3.1. Subject Characteristics

- a) **Number of Subjects:** This trial will enroll 38 subjects at 10 enrolling sites who meet study inclusion and exclusion criteria as described in Section 3.2.
- b) Gender and Age of Subjects: Male or female subjects aged 18 years or older.
- c) Racial and Ethnic Origin: There are no restrictions on race or ethnicity in this study.

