## Exclusion criteria:

- Prescribed amiodarone or dofetilide at the time of consent.
- Left ventricular ejection fraction ≤40% by any imaging modality: echocardiography, angiography, CMRI, or cardiac nuclear test on the most recent test.
- NYHA heart failure class III or IV at time of consent.
- Prior myocardial infarction at any time in the past.
- Pacemaker dependent rhythm at the time of consent.
- Renal impairment (GFR <30 mL/min/m2).
- Prior diagnosis of severe hepatic impairment.
- Pregnant or plan to become pregnant during the course of the trial (Flecainide has not been adequately studied in pregnant women). Pregnancy test is required for women of child-bearing potential prior to randomization.
- Participating in any other interventional clinical trial.
- Unwilling or unable to cooperate with the protocol.
- Lives at such a distance from the clinic that travel for the consent visit would be unusually difficult.
- Decisionally impaired adults, those of questionable capacity, those who cannot manage taking the study drug per the prescribed regimen, and those who cannot consent for themselves will not be recruited for this study.
- Unwilling to sign the consent for participation.

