## 5.4. Safety Assessments

The assessments that will be performed to evaluate safety include medical history, standard 12-lead ECG, implanted device interrogation and the use of the 7-day ZIO-Patch monitor and will be quantified by:

a) VPBs on 7-day ECG monitoring to determine the possibility of proarrhythmia defined as a 3-fold increase in number of VPBs;

b) Total burden of nun-sustained and sustained (ICD treated and untreated) VT episodes on interrogation of ICDs evaluated after the first week and after the fourth week of study drug administration with a 5-fold increase in number of VT episodes defining proarrhythmia.

c) QRS prolongation on ECG defined as >40ms in comparison to baseline and the new presence of the Brugada pattern of the ECG. We expect 17-29% prolongation of the QRS but prolongation >30% (40ms) will be unusual. The appearance of cove-type Brugada pattern will be monitored.

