# 11. RISK/BENEFIT ASSESSMENT

# 11.1. Potential Risks

## 11.1.1. Potential Risks to Patients Undergoing Treatment with Flecainide

Flecainide is an antiarrhythmic drug approved by the Food and Drug Administration in the US since 1982 to suppress cardiac arrhythmias and is predominantly used for atrial arrhythmias. Flecainide was studied in the CAST trial (Echt et al. 1991) in patients after myocardial infarction with ventricular arrhythmias and was associated with a higher incidence of mortality or non-fatal cardiac arrest (19/323) as compared with its matching placebo (7/318). The most serious adverse reactions reported for flecainide in patients with ventricular arrhythmias were new or exacerbated ventricular arrhythmias which occurred in 6.8% of patients and new or worsened congestive heart failure which occurred in 3.9% of patients. In some patients, flecainide treatment has been associated with episodes of unresuscitatable ventricular tachycardia or ventricular fibrillation. There have also been instances of second- (0.5%) or third-degree (0.4%) AV block. A total of 1.2% of patients developed sinus bradycardia, sinus pause, or sinus arrest. The frequency of most of these serious adverse reactions probably increases with higher trough plasma levels, especially when these trough levels exceed 1.0  $\mu$ g/mL, unlikely to occur with our propose dose of 100 mg bid.

Patients with structural heart disease, treated with flecainide for supraventricular arrhythmias, may be at increased risk for proarrhythmia and cardiac adverse events. The use of

flecainide in these patients has been associated with life-threatening and occasionally fatal ventricular arrhythmias. Therefore, in these patients, especially in the presence of impaired left ventricular function with ejection fraction  $\leq 40\%$ , flecainide should be used with extreme caution, preferably after other antiarrhythmic drugs have been tried or considered inappropriate. Because flecainide has a mild negative inotropic effect, it may cause or worsen congestive heart failure, particularly in patients with cardiomyopathy, pre-existing severe heart failure (NYHA functional class III or IV) or ejection fractions  $\leq 40\%$ . Flecainide should therefore be used cautiously in patients who are known to have a history of congestive heart failure or myocardial dysfunction. When used per current FDA approved prescription information flecainide is considered a safe drug.

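### Section 3.2 lists no exclusion for known Brugada syndrome or a coved-type Brugada pattern on the Visit 0 ECG, although the protocol says flecainide may exacerbate the syndrome

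*Combined protocol and SAP*

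**What the plan says.** Four parts of the combined protocol and SAP bear on this.

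- **Hazard.** Section 1.1.3, on how flecainide acts on sodium channels, gives loss of Nav1.5 function as a pro-arrhythmic setting, "such as in the Brugada syndrome that may be exacerbated by flecainide".
- **Monitoring.** Section 5.4, item (c), counts as a safety measure QRS prolongation and "the new presence of the Brugada pattern of the ECG". It adds: "The appearance of cove-type Brugada pattern will be monitored".
- **Entry.** Section 3.1 limits enrolment to subjects "who meet study inclusion and exclusion criteria as described in Section 3.2". Section 3.2 has cardiac exclusions for LVEF of 40% or less, NYHA class III or IV, prior myocardial infarction and pacemaker dependence. It does not mention Brugada syndrome or a Brugada pattern.
- **Screening and randomization.** Section 5.1.1 obtains a medical history and an ECG at Visit 0 and requires screening tests to be assessed and eligibility confirmed. Under section 8.3 a subject is randomized once the conditions in the electronic system are met. No finding on the Visit 0 ECG is defined as disqualifying.

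**The concern.** The protocol recognises a condition that the study drug may worsen and carries the worry into on-drug monitoring, but does not act on it at entry. Under section 5 each patient receives flecainide 100 mg bid for 28 days and placebo for 28 days in random order, so no randomized subject is assigned to avoid the drug. A patient with the known syndrome, or with a coved-type pattern already on the screening ECG, meets the written criteria as far as this hazard goes.

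Item (c) of 5.4 also counts only a new pattern. One already present at Visit 0 would not be an exclusion under 3.2 and would not count as that safety finding later.

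What is at stake is avoidable exposure of an individual patient. The primary endpoint, the mixed model and the sample size argument are untouched.

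**Working it through.** This is mainly a check of text; the only arithmetic concerns the cost of the fix.

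**1. Is the condition covered anywhere in 3.2?** The section has 9 inclusion items: age, diagnosis, VPB count, defibrillator, beta-blocker, two washout items, agreement to avoid antiarrhythmics, and contraception. It has 13 exclusion items: amiodarone or dofetilide, LVEF, NYHA class, prior infarction, pacemaker dependence, renal, hepatic, pregnancy, other trials, cooperation, distance, capacity, and consent. None names Brugada syndrome, a Brugada pattern or a 12-lead ECG finding of that kind. None gives the investigator a general power to exclude on other medical grounds.

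**2. Does another section close the gap?**

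| Section | What it does | Closes the gap? |
|---|---|---|
| 5.1.1 (Visit 0) | History and ECG obtained; screening tests assessed | No disqualifying ECG finding defined |
| 5.1.2 (Visit 1) | Confirms eligibility | No further ECG criterion |
| 6 (medications) | Disallowed antiarrhythmics | Not about this condition |
| 7 (withdrawals) | Subject's choice, loss to follow-up, too few VPBs | No |
| 8.3 (randomization) | Conditions checked in the electronic system | Form not in the documents |
| 11.2 (protection) | Defibrillator, LVEF, beta-blocker | Brugada not mentioned |

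**3. How does the protocol treat other flecainide hazards that it names?** The picture is mixed.

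- Excluded at entry: section 1.1.3 says "Flecainide can have proarrhythmic effects after myocardial infarction", and 3.2 excludes "Prior myocardial infarction at any time in the past". Section 11.1.1 warns of "pre-existing severe heart failure (NYHA functional class III or IV) or ejection fractions" of 40% or less; 3.2 excludes that LVEF range and "NYHA heart failure class III or IV at time of consent".
- Named but not excluded as such: 11.1.1 also urges caution in structural heart disease, cardiomyopathy and a history of heart failure. These stay eligible, and the trial population is itself a cardiomyopathy.

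The comparison shows that exclusion at entry is a tool the protocol already uses. It does not show that Brugada syndrome is the only named hazard left out.

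**4. When do the existing protections act?** The first remote interrogation is one week after the drug is started, and DSMB review follows collected data. The defibrillator treats an arrhythmia once it occurs. All three come after the first dose. The Visit 0 ECG comes before it.

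**5. What could an exclusion cost in power?** Inputs from section 14.1: a 40% reduction, SD of log2(VPB) 1.28, correlation 0.5, n = 34, two-sided 0.05 paired t-test.

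- Shift: -log2(1 - 0.40) = 0.737.
- SD of change: 1.28 × √(2 × (1 - 0.5)) = 1.28.
- Noncentrality at n = 34: (0.737 / 1.28) × √34 = 3.357, with 33 degrees of freedom. Power is 90.3%, which reproduces the stated 90%.
- If one evaluable subject were lost and not replaced (n = 33): 89.4%. If two (n = 32): 88.4%.

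The exclusion would apply before randomization, so a declined candidate is replaced by the next one, and 38 randomized with 34 evaluable stays the plan.

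**The case against.** The strongest reply has four parts.

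- **The hazard statement is background.** It illustrates sodium-channel pharmacology, and the risk sections (11.1 and 11.2) do not name Brugada syndrome. No document says that it occurs in ARVC patients with a defibrillator, so the number affected could be zero. This stands as a limit on size. It does not remove the point, because 5.4(c) brings the concern into the trial's own procedures.
- **The protocol does not exclude every hazard it names.** It excludes some and manages the rest with the defibrillator, expected beta-blocker use and monitoring. This stands, and a charge of plain inconsistency would be too strong. The case rests instead on a screening ECG that is already taken and an exclusion that costs almost nothing.
- **The system or the investigator may stop such a patient.** A reader might infer that nothing would prevent randomization. The documents do not support that: the form and its coded conditions cannot be seen, and the lack of a discretion clause does not oblige an investigator to enrol anyone. What can be said is that the written criteria contain no such bar. With 10 sites, it is better written down than left to individual judgement.
- **A baseline reading is implied.** To call a pattern new, someone must know the Visit 0 state. That is fair, but knowing the state is not the same as acting on it at entry.

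A reader might also infer that the timing of the first on-drug 12-lead ECG, at three weeks, measures this gap. It does not. That timing belongs to the monitoring in 5.4(c), is the same with or without an entry exclusion, and is not criticised here.

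**Conclusion.** The point holds in a limited form. Section 3.2 has no exclusion for known Brugada syndrome or a coved-type pattern at Visit 0, the protocol itself names flecainide as a possible aggravator, and every randomized subject is assigned the drug. Under the written criteria such a patient is eligible for exposure, and the existing safeguards act only after dosing starts.

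The conclusion assumes that eligibility is judged against 3.2, as section 3.1 says, and that the unseen eligibility form adds no such item. It is a modest, inexpensive safety improvement that should be made. It does not show that any subject would be harmed or even affected, and no result of the trial depends on it.

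**What to change.** 1. Add to the exclusions in section 3.2: *Known Brugada syndrome, or a coved-type (type 1) Brugada pattern on the Visit 0 12-lead ECG.*
2. Add a present/absent field for this item to the eligibility form, to be completed from the Visit 0 history and ECG before the randomization field can be checked (sections 5.1.2 and 8.3).

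The cost is one line of protocol text and one form field, with no new visit or procedure. The possible downside is losing a few candidates in a rare disease; they can be replaced before randomization, so the planned sample size need not change. The monitoring in 5.4(c) stays as it is.

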# 5.5. Assessment of Subject Compliance

Study drug compliance will be emphasized during each contact with the study subject. Compliance will also be assessed by count of returned study drug and plasma concentrations of flecainide.

# 5.6. Costs to the Subject

Study drug, the ZIO-Patch monitor, ICD interrogation, ECG during in person visit and serum flecainide level will be paid for by study funds.

# 5.7. Payment for Participation

Subjects will not be paid for participation.

## 5.8. Return of Individual Research Results

Research results will not be provided to subjects.

## 6. CONCOMITANT AND DISALLOWED MEDICATIONS

Subjects will be allowed to take any prescribed beta-blocker including: propranolol, metoprolol, atenolol, nadolol, carvedilol, and bisoprolol. Disallowed antiarrhythmics medications include: sotalol, quinidine, procainamide, disopyramide, lidocaine, phenytoin, mexilitene, propafenone, dofetilide, ibutilide, amiodarone, dronedarone, verapamil, diltiazem. Subjects and their physician treating them for ARVC must agree to discontinue use of these medications to participate in this study for their safety. These medications could be administered after participation of a subject is completed per physician discretion.

## 7. SUBJECT WITHDRAWALS

Subjects will be advised in the written informed consent forms that they have the right to withdraw from the study at any time without prejudice. Subjects may be withdrawn as lost to follow-up by the investigator if they do not follow-up after 4 documented attempts to contact the subject. These subjects will not undergo any additional study activities prior to withdrawal. Subjects not meeting eligibility criteria of at least 500 VPBs in 24-hour Holter after washout of medication used prior to study drug initiation will be withdrawn and replaced.

# 8. STUDY DRUG ADMINISTRATION/ASSIGNMENT

## 8.1. Study Drug

This study is IND exempt per FDA; meeting the criteria set forth in 21 CFR 312.2(b) and 320.31(b). The University of Rochester Investigational Drug Service (IDS) will prepare and dispense the study medication. All capsules of study drug will be identical in appearance (same size and color). Blinded capsules will be prepared via over-encapsulation. Active doses will

consist of 2 x 50 mg flecainide tablets placed inside larger opaque colored capsules and backfilled with lactose. Placebo doses will consist of the same opaque colored capsules filled with inert powder (lactose). Study subjects will be instructed to swallow all capsules whole and not to open them. Each subject will be dispensed 56 blinded doses per treatment period, per randomization (2 doses/day x 28 days = 56 doses per period). The University of Rochester Investigational Drug Service (IDS) will receive the subject randomization assignment and prepare and ship study drug directly to the subject for next day delivery via Federal Express. At the time of crossover and at the study closeout, bottles will be collected for study drug accountability. Subjects will be provided a pre-paid mailer to return unused study drug to the University of Rochester IDS.

# 8.2. Dosage of Study Drug

The active dosage of study drug is two 50 mg tablets of flecainide over encapsulated. The matching placebo will be filled with inert lactose.

## 8.3. Subject Enrollment/Randomization

The University of Rochester IDS will package the capsules into blinded labeled bottles. Site personnel will randomize subjects by using a computer by entry of subject data to confirm eligibility in the study electronic data capture system. If all conditions are satisfied in the computer, the subject is randomized by checking a field on the eligibility form. The site will then send via facsimile subject contact information to the University of Rochester IDS. University of Rochester IDS will dispense study medication per the randomization assignment and ship study drug via Federal Express for next day delivery.

## 8.4. Accountability of Investigational Supplies

At the time of crossover and at the study closeout, the study subject will ship the study drug containers back to the University of Rochester IDS for study drug accountability.

#### 8.5. Subject Withdrawal of Study Drug

This is intention to treat trial. If the subject decides not to take study drug, the subject may remain in the study and continue study procedures for the duration of their participation.

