# **1.2.** Purpose of the Study

The primary specific aim of this pilot trial is to determine whether flecainide administration is associated with a significant reduction in the number of ventricular premature beats (VPBs) in ARVC patients with ICDs.

The secondary aims are to:

- 1) Assess safety of flecainide administration with particular emphasis on pro-arrhythmic response measured by:
  - a. VPBs on ECG monitoring
  - b. Nonsustained and sustained VT/VF episodes documented on ICD interrogation
  - c. Effects of flecainide on QRS morphology and duration.
- 2) Assess the effects of flecainide on the number of VT runs in 7-day ECG recordings.
- 3) Assess the effects of flecainide on the frequency of atrial premature beats in 7-day ECG recordings.
- 4) To demonstrate feasibility of enrollment of rare arrhythmia ARVC patients in a randomized study in preparation for the planned future large clinical trial with VT/VF as the primary endpoint.

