# 5.1.4. Visit 3: Phone visit (One week after initiating study drug)

During this follow-up visit:

• An ICD interrogation (with a manual transmission by patient, if system is not automatic) from remote device monitoring system should be obtained.

- Study drug prescribing regimen, diary and importance of compliance will be reviewed with subject.
- Adverse events will be assessed and reported.
- **5.1.5. Visit 4**: **In person visit in home or in clinic** (Three weeks after initiating study drug) During this follow-up visit:
  - A standard 12-lead ECG recording will be performed.
  - Blood sample will be drawn for flecainide levels. A teaspoon (5ml) of blood is needed for this sample. This blood sample will be sent to a specialized lab. Paper copy of ECG will be uploaded to the Box.com at the University of Rochester.
  - A ZIO-Patch (a small, adhesive, water-resistant one lead ECG recorder) will be applied to the chest for a continuous 24-hour monitoring over 7 days. ZIO-Patch could be self-applied or applied by study staff member. At the end of the 7 days the patch must be removed and returned to the University of Rochester
  - Review study drug prescribing regimen, diary and importance of compliance will be reviewed with subject.
  - Adverse events will be assessed and reported.

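### Two of the three quantified safety criteria rest on one week-3 ECG and one week 3–4 patch per period, and the plan has no rule for recordings made after study drug was stopped

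*Combined protocol and SAP*

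**What the plan says.** Safety is the first secondary aim in Section 1.2: "Assess safety of flecainide administration with particular emphasis on pro-arrhythmic response measured by" VPBs, ICD-documented VT/VF and QRS changes. Section 5.4 turns this into three quantified criteria:

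- (a) "VPBs on 7-day ECG monitoring to determine the possibility of proarrhythmia defined as a 3-fold increase in number of VPBs".
- (b) VT episodes on ICD interrogation, "evaluated after the first week and after the fourth week of study drug administration with a 5-fold increase in number of VT episodes" as the threshold.
- (c) "QRS prolongation on ECG defined as >40ms in comparison to baseline and the new presence of the Brugada pattern of the ECG".

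The recordings behind (a) and (c) are scheduled once per period. At Visit 4 (week 3) and again at Visit 8 (week 8, three weeks into Period 2), "A standard 12-lead ECG recording will be performed", and the ZIO-Patch "will be applied to the chest for a continuous 24-hour monitoring over 7 days". Table 2 shows no other on-treatment ECG or patch, and none is triggered by stopping drug.

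On stopping, Section 8.5 states: "This is intention to treat trial. If the subject decides not to take study drug, the subject may remain in the study and continue study" activities. Section 14.2 fits a mixed model to available data from all randomized subjects and says that similar methods apply to secondary outcomes. Neither 5.4 nor 14.2 says how to classify an ECG or patch recorded after drug was stopped. Sections 5.1.3 and 5.1.7 call for the first-dose date of each bottle. No section asks for the last-dose date or the reason for stopping.

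**The concern.** Following everyone as randomized is a sound choice for efficacy. For a harm criterion it works differently. If a drug provokes arrhythmia or conduction change in the first two weeks and the subject stops because of it, the single scheduled recording comes too late to show it. Under Section 8.5 that recording still belongs to the flecainide period, and it looks like untreated rhythm. If the subject leaves instead, there is no recording. Either way, criteria (a) and (c) cannot flag the event.

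Where stopping is caused by a drug effect, the loss falls on flecainide periods, so it pulls these two criteria towards showing no harm. Section 1.1.4 calls the safety assessment of major importance in view of CAST and intends the pilot to inform a larger trial. With 38 subjects the expected number of cases is small, and one or two missed cases could change what the safety table appears to say.

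**Working it through.** **Plan's own figure.** The plan gives no figure for early stopping or for expected proarrhythmia in this trial. Its power figures are not in dispute here.

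**Step 1: when each safety source is read.**

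| Source | Time within the period | Affected by stopping before week 3? |
|---|---|---|
| 12-lead ECG, criterion (c) | week 3 | Yes |
| ZIO-Patch, criterion (a) | weeks 3–4 | Yes |
| ICD, criterion (b) | after weeks 1 and 4 (Section 5.4) | Early VT can still be captured |
| Adverse events | every contact from Visit 3 | No |

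**Step 2: what counts as off drug by the plan's own washouts.** Visit 4 falls on about day 21 (±2 days). Section 5.2 uses a 7-day washout between periods, and Section 5.1.1 requires at least 5 days before entry.

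- 21 − 7 = day 14, and 21 − 5 = day 16. A subject who stops by day 14 (or day 16) has completed that washout when the ECG is taken and the patch applied.
- A stop on day 20 completes 5 days on day 25 and 7 days on day 27. The patch week (days 21–28) is then only partly washed out.

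**Step 3: illustration of size.** Inputs: n = 38 (Section 14.1) and 6.8% with new or exacerbated ventricular arrhythmia (Section 11.1.1). Three assumptions are made:

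- The rate applies here, although it comes from patients with ventricular arrhythmias in general.
- Every such subject would have met (a) or (c) on drug.
- A share s stops before week 3 and reads as normal off drug. The documents give no value for s, so the full range is shown.

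Expected affected: 38 × 0.068 = 2.58. Missed: 2.58 × s. Chance that at least one case remains visible: 1 − (1 − 0.068 × (1 − s))^38.

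| s | Missed | Still visible | Chance of seeing at least one |
|---|---|---|---|
| 0% | 0 | 2.58 | 93% |
| 25% | 0.65 | 1.94 | 86% |
| 50% | 1.29 | 1.29 | 73% |
| 75% | 1.94 | 0.65 | 48% |
| 100% | 2.58 | 0 | 0% |

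These figures concern criteria (a) and (c) only, not the ICD criterion or adverse events.

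**Step 4: how complete the ICD safeguard is.** At Visit 3, "An ICD interrogation (with a manual transmission by patient, if system is not automatic) from remote device monitoring system should be obtained". Sections 5.4 and 14.3 also call for a reading after four weeks of treatment. Table 2 and the visit descriptions place interrogations at weeks 1, 6 and 10. The second falls one week into Period 2, and the last falls one week after the second bottle ends. The documents do not say how episodes are dated and assigned to a treatment, so these passages must be reconciled. In any case, ICD episode counts do not measure VPBs, QRS width or the Brugada pattern.

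**The case against.** The strongest reply is that the subject in question is seen elsewhere. Someone who stops because of arrhythmia should have an adverse event. Section 10.2 records onset, severity, relationship to drug and action taken at every contact, and Section 14.2 tabulates adverse events by treatment. Criterion (b) is read after week 1, and the DSMB receives ICD, patch and adverse-event data (Section 14.3). Section 8.5 is permissive, so some who stop will leave rather than supply an off-drug recording. The bias needs a chain: a drug effect, stopping before week 3, staying in the study, and a return to normal by the recording. The documents give no probability for the later links.

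This stands as a limit on the size of the problem. It does not close the gap, because nothing links an arrhythmia-driven stop to the criteria in 5.4.

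A reader might infer three stronger things, none of which the documents support.

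- *That all proarrhythmia measures are confined to weeks 3–4.* Criterion (b) is not.
- *That such a subject is scored as free of proarrhythmia.* No section says so. Failing (a) and (c) does not clear someone who meets (b) or has an arrhythmia adverse event.
- *That the primary estimate is materially inflated.* A 3-fold rise is log2(3) = 1.585. Replacing it with 0 in 6.8% of subjects moves the mean by 0.108, or 21% of the 0.515 target: with a 30% reduction in everyone else, the estimate would be 28% rather than 23%. This requires every affected subject to have a 3-fold VPB rise, stop early, stay and read exactly 0. If half stop, the shift is 0.054. Even 0.108 is only about half a standard error (1.28/√34 = 0.22). Stops for other side effects push the other way: if all of the 11% with dizziness (Section 11.1.1) stopped and lost a 30% reduction, 0.11 × 0.515 = 0.057. The net direction for the primary endpoint is not established.

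**Conclusion.** The point holds for two of the three quantified safety criteria. As written, the plan lets off-drug ECG and patch recordings count as flecainide-period safety data and has no on-drug version to set beside them. Where stopping follows a drug effect, this dilutes a harm signal on VPB increase and on QRS/Brugada change.

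The likely size is one or two subjects: about 0.6, 1.3 or 2.6 missed of 2.6 expected if 25%, 50% or 100% stop before week 3. That rests on a borrowed 6.8% rate and an unknown early-stopping share, so it shows scale and is not a forecast. ICD-recorded VT and adverse events by treatment are partial safeguards.

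This is a cheap improvement to the safety analysis. It is no reason to change the primary efficacy analysis.

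**What to change.** In Sections 5.4 and 14.2:

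1. Record the last-dose date and the reason for stopping in each period. The diary and returned bottle are already collected (Sections 5.1.6 and 5.1.10).
2. Report the VPB and QRS/Brugada criteria for recordings made on drug, beside the all-randomized table. Define on drug by the diary last-dose date, supported by the Visit 4 and Visit 8 plasma level. That sample is taken as the patch goes on, so it confirms exposure at the start of the patch week only. In placebo periods the definition rests on the diary and bottle count.
3. List, as a separate row by treatment, subjects who stopped before the week-3 ECG or patch because of a documented arrhythmia or ECG change. Do not reclassify stops for non-specific symptoms as proarrhythmia. Dizziness alone (11%, or 0.11 × 38 = 4.2 subjects) could outnumber the 2.6 expected arrhythmia cases.
4. Keep the all-randomized mixed model as the primary efficacy analysis.

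The cost is one paragraph and two case-report-form fields, with no new procedure. The on-drug sets will be slightly smaller and are no longer a fully randomized comparison, so they belong beside the all-randomized table and do not replace it.
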